*** Will Usual Care Procedures/Interventions be used?"**

Yes No

If yes, please specify and include a description of what the usual care or expected level of care is at VAPHS (e.g., medications, testing, timing, etc.) for patients, similar to those individuals that meet the inclusion/exclusion criteria for this research study:

Those participants who demonstrate oxygen desaturations during the bedside pulmonary telerehabilitation sessions or during any of the baseline study procedures will be referred for a formal home oxygen evaluation, which would be considered a usual care procedure for any patient demonstrating low oxygen levels.

Pulmonary rehabilitation is likewise considered standard of care for patients with COPD. This is traditionally performed in a facility-based setting, although a growing interest in pulmonary telerehabilitation has developed over the past several years, particularly given the inaccessibility of facility-based programs to a large number of patients. VAPHS currently does not have a facility-based pulmonary rehabilitation program. We are working toward developing a pulmonary telerehabilitation program that we can offer our COPD patients but resources will be limited. Most COPD patients do not enroll in facility-based pulmonary rehabilitation programs in the weeks following hospitalization for an acute exacerbation of COPD.

2.1 If Usual Care Procedures/Interventions will be used, who is the individual or entity responsible for relevant aspects of the usual care (i.e., which of the above usual care activities will the research study team be responsible for)?:
The study team will be responsible for placing the inpatient consult for the home oxygen evaluation prior to discharge. The study team will be fully responsible for the inpatient pulmonary rehabilitation and pulmonary telerehabilitation sessions.

2.2 Does the usual care at VAPHS for the condition of interest in this research study differ from national guidelines/recommendations (i.e. standard of care)?

Yes No

If yes, please describe the differences:

2.3 Are any procedures that are considered standard for this patient population performed more frequently than usual care?

Yes No

If yes, please indicate which time points are considered usual care and which are considered research.

2.4 If there is more than one standard, does VAPHS limit which one is followed (e.g. warfarin use for atrial fibrillation vs. one of the newer anticoagulants?).

Yes No

If yes, please explain:

3.0

*** Does clinical expertise need to be enlisted?**

Yes No

If yes, please provide the provisions for enlisting the services of a clinician with appropriate expertise and privileges to perform duties, if the investigator is not a clinician [i.e. reviewing the data, adverse events, and new study findings; also making required decisions to protect the health of the subject (e.g., stopping the participant's involvement in the study or determining when to notify the subject or the subject's health care provider of information that may affect the health of the subject)]:

4.0 Please upload any surveys, questionnaires, and data collection forms.

Document	Description	Version Number
View Six Minute Walk(0.01)		0.01
View 60 SECOND SIT TO STAND(0.01)		0.01
View Baseline Visit Checklist(0.02)		0.02
View BORG SCALES(0.01)		0.01
View Follow up Visit Checklist(0.02)		0.02
View Home Based Pulmonary Rehab(0.01)		0.01
View Muscle Strength Form Hand Grip Strength/ Leg Press (0.01)		0.01

View Participant Information Form_telerehab.docx(0.02)	0.02
View Participant Screening Sheet. Inclusion_Exclusion(0.03)	0.03
View Pedometer Diary Patient(0.01)	0.01
View Pedometer Weekly Documentation (0.01)	0.01
View Pulmonary Telerehabilitation Participation Survey.docx(0.02)	0.02
View sf36.pdf/ Medical Outcomes(0.02)	0.02
View SGRQ(0.04)	0.04
View sit to Stand(0.01)	0.01
View Vitals Form(0.01)	0.01

ID: Pro00002952

View: 4.1 Research study methods: analysis Plan

1.0 * Please describe the analysis plan for the study (it is acceptable to refer to the sponsor/multi-site protocol for section if applicable):

The distributional characteristics of the outcome measures and change in outcome measures between study groups will be determined using appropriate descriptive statistics (e.g. mean, median, standard deviation, range) and graphical summarizations (e.g. histograms, boxplots, line plots). The purpose of this pilot study is to generate preliminary data on the expected effect size and variance of the outcome measures to facilitate planning (i.e. sample size calculations and power analyses) of a larger, randomized controlled trial. As such, we acknowledge that, given our small sample size (n=30, 15 participants per group), we likely will not have the power to detect a significant statistical or clinical difference in outcome measures between the intervention and usual care groups. However, we will perform exploratory analyses to compare changes in outcome measures between groups using a Student's t-test or nonparametric tests when appropriate.

ID: Pro00002952

View: 5 Sub-Studies

1.0 * Is there a sub-study or are there sub-studies associated with this study?

There is no sub-study associated with this study.

ID: Pro00002952

View: 6 Study Population Summary

Study Population Summary

1.0 * What is the maximum number of subjects you plan to enroll at VAPHS?

We plan to enroll 38 participants, accounting for 25% attrition, to result in 30 participants (15 intervention, 15 control) completing baseline and eight-week follow up testing.

2.0

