SA 2: To determine physical activity levels and the magnitude and variability in changes of measurements of muscle strength, functional exercise performance, and health-related quality of life following an eight-week home-based pulmonary telerehabilitation program versus usual care initiated in veterans with moderate to severe COPD immediately following hospitalization for an AECOPD.

Hypothesis: Participants randomized to an eight-week, three times per week pulmonary telerehabilitation program will demonstrate increased physical activity levels and greater improvement in maximal handgrip and quadriceps muscle strength, six minute walk, one-minute sit-to-stand testing, and health-related quality of life scores at completion of the intervention compared to participants randomized to usual care. We will compare changes from baseline in physical activity levels measured by pedometer, maximal handgrip and quadriceps muscle strength, six minute walk, one-minute sit-to-stand repetitions, and St. George's Respiratory Questionnaire and Short-Form 36-item questionnaire scores in veterans with moderate to severe COPD following an eight-week pulmonary telerehabilitation program versus usual care initiated after hospitalization for an AECOPD. The effect size and variance of these measurements will be used for the statistical planning (i.e. sample size and power calculations) of a larger, randomized controlled trial.

4.0 * Provide a summary of the background of the study, and explain how this research will contribute to existing knowledge. Describe previous studies that provides a basis to show that the proposed research can be carried out without undue risk to human subjects.

Chronic obstructive pulmonary disease (COPD) is the third leading cause of death in the United States and is highly prevalent in the aging veteran population. Health care costs in COPD are largely attributable to

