*** Research Procedures/Interventions:**

Study Interventions:

Pulmonary Telerehabilitation Intervention Group: The intervention will consist of an eight-week, three sessions per week, home-based pulmonary telerehabilitation program that will incorporate both lower extremity endurance exercise and upper and lower extremity resistance training. **Subjects randomized to the study intervention will also participate in a optional once monthly support group via group phone call through a reserved VANTS line. This phone conferencing consisting of an educational topic (i.e. inhaler use, understanding COPD) and group discussion.** Participants randomized to the intervention arm will receive a tablet with VA Video Connect software installed for video conferencing, a portable cycle ergometer, and a set of exercise resistance bands of varying resistance (extra-light, light, medium, heavy, extra-heavy). **Patients will also be given an pedometer at hospital discharge to be worn everyday following discharge to track the patient's physical activity. Patients will receive a pedometer diary from study staff to record their daily steps from the pedometer.** We also contact participants by telephone weekly to document their pedometer count. They will be permitted to keep the pedometer, cycle ergometer and resistance bands, at the completion of the study.

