For safety purposes, participants in both the intervention and usual care group will also be enrolled in the hospital's telehealth program, which consists of daily monitoring of pulse oximetry, heart rate, blood pressure, and weight and regular contact with a telehealth provider. They will receive a pulse oximeter, automated blood pressure cuff, and scale as part of this program. An exercise physiologist will meet with participants randomized to the intervention group prior to hospital discharge but after informed consent is obtained to conduct a minimum of one to two face-to-face inpatient bedside pulmonary rehabilitation sessions. These sessions will be used to guide development of an individualized exercise prescription, determine participant oxygen requirements with exercise, and to assess participant safety. **Within one to six weeks post-discharge, participants in the intervention arm will begin pulmonary tele rehabilitation** sessions via 1:1 video conferencing with the exercise physiologist/study coordinator. The exercise physiologist/study coordinator will be located at VAPHS during these video conferencing sessions. These sessions will consist of: (1) a brief pre-exercise interview to assess symptoms and vital signs (pulse oximetry, pulse, blood pressure); (2) a warm-up period consisting of upper and lower extremity stretching exercises; (3) cycle ergometry with resistance settings and goal duration determined by the individualized exercise program developed prior to hospital discharge; (4) upper and lower extremity strength training with resistance bands; (5) a post-exercise debriefing interview to assess symptoms and post-exercise vital signs. Subjects will be offered the opportunity to enroll in a traditional facility-based pulmonary rehabilitation program.

Usual Care Group: Participants randomized to the usual care arm will also be enrolled in our institution's telehealth program, will receive an automatic blood pressure monitor, portable pulse oximeter, and scale. **Patients randomized to Usual Care will also be given an pedometer at hospital discharge to be worn everyday following discharge to track the patient's physical activity. Patients will receive a pedometer diary from study staff to record their daily steps from the pedometer.** We

also contact participants by telephone weekly to document their pedometer count. They will be permitted to keep the pedometer at the completion of the study.

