Development of the Initial Exercise Prescription: The exercise prescription will be developed based on exercise performance and self-reported modified Borg dyspnea scores, a scale widely used in both the clinical and research setting to measure a patient's perceived shortness of breath and effort, during the six minute walk and bedside pulmonary rehabilitation sessions. During the bedside sessions, the exercise physiologist/study coordinator will select the resistance setting on the cycle ergometer that allows the participant to perform five minutes of lower extremity cycle ergometry while achieving Borg scale ratings between four and six in accordance with the American Thoracic Society (ATS)/European Respiratory Society (ERS) Guidelines. Alternatively, interval training, which has resulted in similar improvements in walk distance and quality of life scores, will be used for those participants unable to perform five minutes of cycle ergometry. During the resistance training exercises, the resistance band workload that causes fatigue after eight to twelve repetitions will be selected for each target muscle group. Exercise performance during these bedside sessions combined with heart rate and exercise performance during six minute walk will be used to develop an individualized exercise prescription for home pulmonary telerehabilitation. [name] will provide guidance as needed on developing the initial exercise prescription for each participant.

Modification of the Exercise Prescription: The exercise prescription will be adjusted during the eight-week intervention to achieve modified Borg dyspnea scores of four to six during cycle ergometry and to target one to three sets of eight to twelve repetitions of each resistance training exercise per established guidelines. The resistance band level will be increased when a participant is able to complete three sets of twelve repetitions using correct technique through the full range of motion. [name] will provide guidance as needed on modification of the individualized exercise prescriptions throughout the eight-week intervention for each participant based on their performance. Other factors, including heart rate and blood pressure during exercise, will be considered when modifying the exercise prescriptions.

Measurement of physical activity: Participant activity will be measured with an pedometer provided at hospital discharge. The pedometer will be worn every day to track the participant's physical activity.

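### Weekly step counts are collected from both arms, but the plan names no analysis that uses the repeated weeks or keeps participants with partial data

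*Combined protocol and SAP*

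**What the plan says.** **Collection.** Under Research Procedures/Interventions (View 4), the intervention arm is given a pedometer at discharge. "Patients will receive a pedometer diary from study staff to record their daily steps from the pedometer", and "We also contact participants by telephone weekly to document their pedometer count". The usual care arm has the same arrangement: "Patients randomized to Usual Care will also be given an pedometer at hospital discharge to be worn everyday following discharge", with a diary, and staff "also contact participants by telephone weekly to document their pedometer count". The list of data collection forms includes a patient diary and a weekly pedometer form. Measurement starts at discharge: "Participant activity will be measured with an pedometer provided at hospital discharge".

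**Contrast.** Specific Aim 2 (View 2) states: "We will compare changes from baseline in physical activity levels measured by pedometer". It does not say which days form the baseline or the end value.

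**Analysis.** View 4.1 plans descriptive statistics and graphs, line plots among them. It then says "we will perform exploratory analyses to compare changes in outcome measures between groups", by Student's t-test or nonparametric tests. It works with n=30, 15 per group, and says power is likely to be inadequate. It gives the pilot's purpose as estimating effect size and variance for a larger trial.

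**Sample.** View 6, item 1.0: "We plan to enroll 38 participants, accounting for 25% attrition", so that 30 complete baseline and eight-week testing. Intention to treat appears once, in the lay summary, with no analysis rule attached.

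**The concern.** The walk, strength, sit-to-stand and questionnaire measures are planned before and after. Quadriceps testing also needs an optional early return visit. Steps are different: they are reported week by week, by telephone, without a visit. A participant who stops reporting after week 5 has five weekly means on record.

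The stated test needs one change per person. If that change is taken from the first week to the last, the early leaver contributes nothing and the intermediate weeks of everyone else go unused in the comparison.

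Two things are at stake:

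- **Planning estimates.** These are what the pilot is meant to deliver. A single change per person yields only the SD of that change. It does not separate between-person from within-person variance, which a larger trial collecting weekly steps would need.
- **Selection.** The trial is unblinded, and a participant who arranges facility-based rehabilitation must discuss withdrawal. Leaving may therefore be related to activity or motivation, and a completer comparison has no protection against that.

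**Working it through.** **The plan's enrolment figure.** 30 × 1.25 = 37.5, rounded up to 38, which reproduces the stated number. Dividing instead gives 30 / 0.75 = 40. At a true 25% attrition, 38 × 0.75 = 28.5 would complete. The plan's own pair, 30 of 38, implies 8 / 38 = 21% attrition. A completer analysis would therefore omit 8 (38 − 30) to about 10 (38 − 28.5 = 9.5) participants. The plan has no power calculation to reproduce.

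**Assumptions.** The documents give no step SD or correlation. Assumed here: eight weekly means of equal variance (set to 1), equal correlation r between any two weeks with r from 0.5 to 0.8, 19 participants per arm, and 25% dropout at random.

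**Complete data, variance per person.**

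- Week 8 minus week 1: 2(1 − r).
- Mean of weeks 5-8 minus week 1: (1 − r)(1 + 1/4) = 1.25(1 − r).
- Ratio: 1.25 / 2 = 0.625 at any r.

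**With 25% dropout.** The comparator is a completer week-8-minus-week-1 change. The alternative is a mixed model on every reported week (week as a factor, random participant intercept). Averaged over simulated dropout patterns, the variance ratios are nearly constant over r = 0.5 to 0.8:

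| Contrast from the mixed model | Variance relative to completer change |
|---|---|
| Week 8 minus week 1 | about 0.90 |
| Weeks 5-8 minus week 1 | about 0.50 |

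**Plausibility.** If the partial weeks recovered everything, the first ratio would be 28.5 / 38 = 0.75; if they recovered nothing, 1. For the second, the limits are 0.625 × 0.75 = 0.47 and 0.625. Both results lie inside their limits. Most of the gain in the second row thus comes from averaging later weeks (0.625) and the rest from partial data (0.50 / 0.625 = 0.80).

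**Why the contrast must refer to an early week.** The mean of all eight weeks without an early reference has variance r + (1 − r)/8. Against 2(1 − r):

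| r | All-week mean | Week-8-minus-week-1 change |
|---|---|---|
| 0.5 | 0.5625 | 1.00 |
| 0.7 | 0.7375 | 0.60 |
| 0.8 | 0.825 | 0.40 |

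Setting the two equal gives 23r = 15, so r = 0.65. Above that the plain average is less precise. With 25% dropout at r = 0.8 it has about 1.53 times the variance of the completer change, even though it uses all participants.

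**Time axis.** View 4 starts telerehabilitation one to six weeks after discharge. View 12.2 describes pedometer wear for eight weeks. A start at six weeks puts the end of an eight-week programme at 6 + 8 = 14 weeks, with only the last two of eight pedometer weeks on the programme (8 − 6 = 2).

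**The case against.** The strongest case against is that the plan does not say what it might be charged with. A reader might infer that steps are reduced to one first-to-last change and that everyone who stops early is discarded. Neither is written. The step change is undefined and could average several weeks. No exclusion of partial data is stated, and line plots would display the weekly course. The 25% attrition refers to completing baseline and eight-week testing, so someone who misses that testing may still report steps by telephone. It does not follow that 9 or 10 participants lose all their step data. All this stands, and it limits the point to an omission.

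It is also tempting to claim that an eight-week mean cuts variance by 18% to 44% (1 − 0.825 to 1 − 0.5625). That compares it with a single week's value, which the plan does not propose to analyse. Against a change score the plain average can be worse, as shown above. Where the programme starts late, it would also mix pre-programme weeks into the arm difference.

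Two further objections stand in part. The tests are exploratory in a small pilot, so no confirmatory claim is at risk; but the effect size and variance are the product, and these are what the omission affects. A mixed model is also no cure for attrition: it limits bias only if dropout is explained by the steps already reported, and withdrawal for facility-based rehabilitation may not be.

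**Conclusion.** The point holds as an omission and is a worthwhile improvement rather than a flaw that threatens the trial. Weekly steps are collected in both arms, yet the only stated comparison is a two-group test on changes, with no repeated-measures analysis and no rule for partial data.

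Under equal correlation and random dropout, a model on all reported weeks has about 0.90 of the completer variance for the same week-8-minus-week-1 contrast. The figure of about 0.50 for weeks 5-8 minus week 1 also changes the quantity estimated, so it is a gain only if the average over later weeks is of interest. If neighbouring weeks are more alike than distant ones, these ratios will differ. The documents do not support saying that early leavers are discarded by design.

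**What to change.** Add to the analysis plan (View 4.1):

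- **Data.** Weekly mean daily steps for all randomised participants, using every reported week. Unreported weeks are missing, not zero.
- **Model.** Linear mixed model with arm, week, arm-by-week and a random participant intercept.
- **Estimate.** Arm difference in change from the first post-discharge week to the later weeks, which are to be named in advance, with 95% CI. It should not be an unadjusted average over all weeks since discharge.
- **For the next trial.** Report between-person and within-person variance.
- **Limits to state.** The first post-discharge week follows randomisation and, in the intervention arm, the bedside sessions, so it is an early reference rather than a true baseline. The model assumes that dropout is explained by reported steps.

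Separately, reconcile the eight-week pedometer period in Participant Payments with the one-to-six-week range for starting telerehabilitation in Research Procedures, so that the step window and a time zero common to both arms are defined.

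The analysis change costs a little more analysis work and requires no new data or visits.

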*** Abstract. Please provide a brief description of the study.**

Pulmonary telerehabilitation programs have been shown to have a high acceptance and adherence rate and lead to improvement in exercise capacity and quality of life in stable COPD. However, data regarding the feasibility and impact of pulmonary telerehabilitation following hospitalization for an AECOPD on physical activity levels, muscle function, exercise capacity, and health-related quality of life are lacking. Our primary hypothesis is that a home-based pulmonary telerehabilitation program initiated at hospital discharge following an AECOPD is feasible in the veteran population and will result in increased physical activity and greater improvement in muscle function, exercise capacity, and health-related quality of life compared to usual care. We will test this hypothesis with the following specific aims: (1) To determine the feasibility of an eight-week home-based pulmonary telerehabilitation program in veterans with moderate to severe COPD initiated in the immediate post-hospitalization period following an AECOPD. (2) To determine physical activity levels and the magnitude and variability in changes of measurements of muscle strength, functional exercise performance, and health-related quality of life following an eight-week home-based pulmonary telerehabilitation program versus usual care initiated in veterans with moderate to severe COPD immediately following hospitalization for an AECOPD. We will randomize (1:1 allocation) 30 male and female veterans hospitalized with an AECOPD to either an eight-week, three sessions per week, home-based pulmonary telerehabilitation program that includes lower extremity endurance exercises with a cycle ergometer and upper and lower extremity strength training with 1:1 supervision via video conferencing with an exercise physiologist as well as an optional once -monthly support group via teleconferencing versus usual care. Changes from baseline in physical activity levels, handgrip and quadriceps muscle strength, exercise endurance, and health-related quality of life will be assessed following the pulmonary telerehabilitation program versus usual care. Findings from this project will contribute to the growing field of pulmonary telerehabilitation and will provide critical preliminary data for the design and implementation of a larger, randomized control trial assessing the impact of pulmonary telerehabilitation on long-term clinical outcomes following AECOPD.

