Participants will be in regular contact with a telehealth provider. A study team member will meet with participants randomized to the usual care arm prior to discharge but after informed consent is obtained to discuss the importance of exercise and will encourage exercise (strength training, light aerobic activity such as walking or cycling) a minimum of 20-40 minutes three times per week at discharge. **The usual care group will not receive a cycle ergometer or resistance bands and will not participate in the VANTS conference call support group. Patients randomized to the control group will be offered home telerehab enrollment following completion of the study.**

Subjects in both the intervention and usual care group will receive all of the necessary information needed to participate in regular pulmonary rehabilitation. If an enrolled subject arranges to begin participation in a facility-based pulmonary rehabilitation before the conclusion of the study period, the subject will need to contact the study team to discuss withdrawal from study participation.

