Safety and Oxygen Monitoring: Oxygen saturations will be continuously monitored during the six minute walk testing and inpatient bedside pulmonary rehabilitation sessions. Any participant demonstrating oxygen desaturations during these activities will undergo a formal exercise desaturation study to determine oxygen requirements prior to hospital discharge. In addition, vital signs will be monitored before, during, and after each bedside pulmonary rehabilitation session. These sessions will allow investigators to assess participant safety with exercise and to disqualify any participants that are unable to participate safely in endurance and/or resistance training. Finally, participants will be provided an automated blood pressure cuff and pulse oximeter to allow for intermittent monitoring of blood pressure and continuous monitoring of oxygen saturation and heart rate during the home pulmonary telerehabilitation sessions. Prior studies have shown home-based pulmonary telerehabilitation programs to be safe, even in severe COPD. However, if the exercise physiologist has any concern with participant safety during the home-based telerehabilitation sessions, emergency services will be immediately contacted.

Handgrip and quadriceps muscle strength testing: Handgrip strength of the dominant hand will be measured with a hand dynamometer. Three measurements will be taken with a 60 second recovery period between trials. The average maximal force across trials will be calculated as the final handgrip strength. Quadriceps muscle maximal force (kilogram-force, kgf) will be measured with a Keiser leg press, equipment available in [name] research center, in those participants willing to return within approximately one week post-discharge for muscle strength measurements. This test will be optional. One repetition maximum (1RM) measures will be obtained by progressively increasing resistance until the participant is unable to successfully complete one repetition. Peak muscle power will be measured at 40, 50, 60, 70, 80, and 90 percent of the 1RM 30 minutes after the 1RM measurement was obtained.

Six Minute Walk testing:

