*** Do you plan on enrolling patients into different categories:**

Yes No

If yes, please explain:

We will randomize 30 eligible participants hospitalized with an acute exacerbation of COPD in a 1:1 allocation to either the eight-week home-based pulmonary telerehabilitation program intervention versus usual care prior to hospital discharge.

3.0 If this is a multi-site study, indicate the projected total subject accrual:

N/A

4.0*** Please provide a justification for the sample size:**

To meet our recruitment goal of 30 subjects over a one-year time interval, we will be required to enroll an average of 2-3 participants per month. A review of our COPD admission data shows that the medicine service at the VAPHS admits a mean of 28.4 (SD 8.7, range 15-43) patients per month with a primary diagnosis of COPD with acute exacerbation. Therefore, we anticipate no difficulty with recruitment for this study. We have not performed a sample size calculation given that this is a pilot study to generate preliminary data for the planning of a larger randomized controlled trial (including data to calculate estimated sample size).

ID: Pro00002952

View: 6.1 Study Population

Study Population**1.0 * Check all that apply to describe your study population:**

Study Population

 Non-Veterans Special Populations **Veterans** Vulnerable populations Other**2.0 * Indicate the inclusion criteria for enrollment:**

(1) Male and female veterans age 40-80; (2) Moderate or severe COPD with a forced expiratory volume in 1 second - forced vital capacity ratio (FEV1/FVC) < 0.70 and FEV1 < 80% predicted; (3) Hospitalization with a primary diagnosis of AECOPD, defined as an increase in shortness of breath, cough, and/or sputum production beyond the normal day-to-day variation necessitating a change in regular medication when other causes of increased shortness of breath, cough, and/or sputum production have been ruled out; (4) Capable of operating a tablet independently with adequate vision and hearing. The inclusion criteria should select for COPD patients with significant pulmonary disease that fall within an age range where age-related changes in muscle function are not the dominating factor.

3.0 * Indicate exclusion criteria for enrollment:

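### Enrolling 38 with 25% attrition gives 28.5 expected completers, not 30, and the plan uses 30 both as the number randomised and as the number completing

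*Combined protocol and SAP*

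**What the plan says.** Five places in the combined protocol and SAP bear on the sample size.

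- Study Population Summary, item 1.0, on the maximum enrolment: "We plan to enroll 38 participants, accounting for 25% attrition, to result in 30 participants (15 intervention, 15 control". The sentence goes on to define the 30 as those completing both baseline and eight-week testing.
- Study Population Summary, item 2.0: "We will randomize 30 eligible participants hospitalized with an acute exacerbation of COPD in a 1:1 allocation", with randomisation placed before discharge.
- Study Population Summary, item 4.0: "To meet our recruitment goal of 30 subjects over a one-year time interval", for which an average of 2-3 enrolments per month is said to be required. The same item reports a mean of 28.4 admissions per month for COPD exacerbation and states that no sample size calculation was made.
- Study Summary, item 2.0 (Abstract): "We will randomize (1:1 allocation) 30 male and female veterans hospitalized with an AECOPD".
- Research Study Methods, analysis plan (4.1): "given our small sample size (n=30, 15 participants per group", as the basis for the effect-size and variance estimates.

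Research Study Methods, item 1.0, also provides for losses after randomisation. On the bedside sessions it says: "An exercise physiologist will meet with participants randomized to the intervention group prior to hospital discharge but after informed consent is obtained". Under Safety and Oxygen Monitoring, those sessions allow the investigators "to disqualify any participants that are unable to participate safely in endurance and/or resistance training". If an enrolled subject arranges facility-based rehabilitation before the study period ends, "the subject will need to contact the study team to discuss withdrawal from study participation".

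**The concern.** There are two problems. First, the stated attrition applied to the stated enrolment does not give the stated number of completers. Second, 30 serves as the number randomised, the number recruited in a year, the number completing week 8 and the number analysed, while 38 is the number enrolled. Thirty can be both randomised and completing only if nobody is lost after randomisation, and the plan's own procedures allow for such losses.

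The pilot exists to estimate effect sizes and variances for a larger trial and, under its first aim, to assess feasibility. For both purposes the counts of people enrolled, randomised and completing should be unambiguous. Nothing confirmatory is at stake: the plan makes no power claim and says it is unlikely to detect a difference.

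**Working it through.** **Inputs.** Enrolled 38, attrition 25%, target 30 completers (Study Population Summary, 1.0). Randomised 30 (same section, 2.0, and Abstract). Recruitment goal 30 in 12 months, required rate 2-3 per month, 28.4 admissions per month (same section, 4.0). Analysis n of 30, 15 per group (analysis plan, 4.1).

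**Step 1. Reproduce the plan's 38.** 30 × (1 + 0.25) = 37.5, rounded up to 38. The likely source is therefore adding 25% to the target. To allow for losing 25% of those enrolled, one divides by the fraction retained: 30 / (1 − 0.25) = 40.

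**Step 2. Expected yield from 38.** 38 × 0.75 = 28.5, or 19 × 0.75 = 14.25 per arm. To get 30 from 38, only 8 may be lost: 8/38 = 21.1%.

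**Step 3. Chance of reaching the target.** Assume each participant independently completes with probability 0.75.

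| Enrolled | P(at least 30 complete) | P(at least 15 complete in one arm) | P(at least 15 in both arms) |
|---|---|---|---|
| 38 (19 per arm) | 0.365 | 0.465 | 0.465² = 0.217 |
| 40 (20 per arm) | 0.584 | 0.617 | 0.617² = 0.381 |

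**Step 4. Effect on precision.** The 95% half-width for a between-arm difference in means, in SD units, is t(0.975, 2n − 2) × √(2/n).

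- n = 15 per arm: 2.048 × √(2/15) = 0.748
- n = 14 per arm: 2.056 × √(2/14) = 0.777, a ratio of 0.777/0.748 = 1.039, about 4% wider

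**Step 5. If 30 is the number randomised.** Suppose the 25% loss applied after randomisation. Then 30 × 0.75 = 22.5 complete, 11.25 per arm, and the half-width at n = 11 is 2.086 × √(2/11) = 0.889 SD. This is conditional, because the plan states the 25% only against the 38.

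**Step 6. Recruitment.** Thirty in a year needs 30/12 = 2.5 per month, 2.5/28.4 = 8.8% of admissions. Thirty-eight needs 38/12 = 3.17 per month, 3.17/28.4 = 11.2%. The stated 2-3 per month thus fits 30 in a year but not 38. At 2-3 per month, 38 would take 38/3 = 12.7 to 38/2 = 19 months. Telerehabilitation may start up to six weeks after discharge and lasts eight weeks, so the last participant needs up to 14 weeks (3.2 months). That gives 15.9 to 22.2 months, inside the two-year project described in Study Summary, item 3.0.

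**The case against.** The best reconciling reading is that 38 consent, 30 are randomised, and all losses come before randomisation. In support, item 1.0 asks for a maximum, so 38 may be only a ceiling, and exclusion criterion 4 uses observation at the bedside sessions, so some enrolled people could count as screen failures. But no section says this. The bedside sessions are described for people already randomised to the intervention, and the 30 in item 1.0 are defined by eight-week follow-up. The reading would also leave no allowance for losses over those eight weeks, and the recruitment goal would still be wrong, since 38 would have to be enrolled.

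The weight of the point is also open to challenge. This is a pilot with no sample size calculation, and one or two completers change little. That stands, and it is why the point is minor. It is also fair that the 11-per-arm figure rests on a reading the plan does not state, and that the probabilities in Step 3 assume equal arms and independent losses; these illustrate and do not carry the conclusion.

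Finally, 2-3 per month is the rate said to be required for 30, not a forecast of what can be achieved, so 12.7 to 19 months is not a prediction. It shows only that the stated rate and a one-year period cannot together deliver 38: one of the two must change.

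**Conclusion.** The concern holds as a minor error. At the plan's own 25% attrition, 38 enrolled gives 28.5 expected completers, a shortfall of 1.5 against the stated 30. This needs no assumption beyond the plan's figures, with attrition read as a fraction of those enrolled. Precision is about 4% worse at 14 per arm than at 15. No power statement, endpoint or decision rule is affected, and with 28.4 admissions per month and a two-year project the recruitment conclusion is little affected.

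The double use of 30 is a real inconsistency: the sections agree only if nobody is lost after randomisation, which the plan does not claim. If 30 were randomised and 25% then lost, 22 to 23 would complete; how far this applies depends on what the sponsor meant.

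**What to change.** - Keep the maximum of 38 and restate the expected yield at 25% attrition as about 28 completers (14 per arm). Change the n of 30 in the analysis plan to match.
- Give one number each for enrolled, randomised and completing, and use them consistently in the Abstract, the analysis plan and Study Population Summary items 1.0, 2.0 and 4.0. Randomising 38 (19 per arm) is the reading that fits attrition through week 8.
- Restate the recruitment need as about 3.2 per month for 12 months, or keep 2-3 per month and state a period of about 13 to 19 months.

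This costs only wording: the stated number of completers falls by about two, and either the monthly rate or the accrual period rises slightly. If the sponsor prefers to keep 15 completers per arm, the alternatives are to enrol 40, which costs two more participants, or to justify an attrition figure of about 21% with 38 enrolled.
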